**Table 1. Summary of Study Procedures**

Time points	ToPIC participants	TTAU participants	Outcome	Compensation
Pregnant Patient Participants:				
Baseline <20 weeks gestation	
 
• Urine cotinine
 
• EACO
 
• ACOG tobacco use screen
 
	
 
• Urine cotinine
 
• EACO
 
• ACOG tobacco use
 
	Eligibility screen for tobacco	\$10
Monthly through end of pregnancy at regularly scheduled prenatal visits	
 
• CTTS tobacco treatment education support, including
 
• Individualized treatment plan (baseline)
 
• 5As
 
• Motivational Interviewing
 
• Navigation to resources
 
	
 
• 5As, as per usual
 
		
28-34 weeks gestation	
 
• Urine cotinine
 
• EACO
 
• TUQ
 
	
 
• Urine cotinine
 
• EACO
 
• TUQ
 
	Tobacco cessation or reduction	\$10
Postpartum 2-8 weeks after delivery	
 
• Urine cotinine
 
• EACO
 
• TUQ
 
	
 
• Urine cotinine
 
• EACO
 
• TUQ
 
	Tobacco cessation or reduction	\$20
Postpartum 12-18 weeks after delivery	
 
• Urine cotinine
 
• EACO
 
• TUQ
 
	
 
• Urine cotinine
 
• EACO
 
• TUQ
 
	Tobacco cessation or reduction	\$20

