## **Study Protocol:**

**Study Design:** The effectiveness-implementation hybrid design of this proposal enables the simultaneous evaluation of both effectiveness outcome measures as well as of the process of implementation. We propose a type 2 hybrid trial to test both the effectiveness of the clinical intervention (the 5A's delivered via a CTTS) while simultaneously gathering multi-level contextual data regarding potential barriers and facilitators to clinical implementation. Effectiveness questions will be explored using a two-armed cluster randomized controlled design. Implementation questions include: (1) what are the facilitators/barriers to delivering tobacco treatment to pregnant women using existing healthcare provider in the clinic settings; (2) how likely is intervention delivered as prescribed (fidelity); (3) what implementation strategies might maximize the facilitators and overcome barriers to implementation; and (4) what potential modifications could be made to maximize implementation? This pilot project will gather quantitative and qualitative data for a mixed-method, multi- stakeholder process evaluation of intervention training and delivery among 12 clinic staff and providers involved in the project. Furthermore, our use of Medicaid claims data will enhance understanding of the strengths and limitations of these data for future evaluations.

**Aim 1 - Effectiveness evaluation:** As part of routine standard of care, all pregnant Medicaid patients who receive first trimester screening through the intervention or Tobacco Treatment as Usual (TTAU) clinic will also be asked about their tobacco use consistent with the ACOG recommended questionnaire (the standard of care for TTAU is the ACOG recommended questionnaire in Box 1. ACOG 5A's). All women who report tobacco use would be considered eligible to participate to receive ToPIC or TTAU. Participants in the intervention and TTAU clinics will be informed their urine will be tested for cotinine to confirm tobacco use at each data collection point and be informed of their results in compliance with ACOG clinical standards. Inclusion criteria are: 1. Pregnant and age 18-44; 2. Tobacco user (self-reported) 3. Can read and write in English; and 4. Medicaid subscriber.

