### **BOX 1. ACOG's 5A's**

1. **ASK** the patient about smoking status at the 1st prenatal visit and follow-up with her at subsequent visits.
  - A. I have never smoked or I have smoked fewer than 100 cigarettes in my lifetime
  - B. I stopped smoking before I found out I was pregnant and I am not smoking now
  - C. I stopped smoking after I found out I was pregnant, but I am not smoking now
  - D. I smoke now, but I cut down on the number of cigarettes I smoke since I found out I was pregnant
  - E. I smoke regularly now, about the same as before I found out I was pregnant
2. **ADVISE** the patient who smokes to stop by providing advice to quit with information about the risks of continued smoking to the woman, fetus, and newborn.
3. **ASSESS** the patient's willingness to attempt to quit smoking at the time. Quitting advice, assessment, and motivational assistance should be offered at subsequent visits.
4. **ASSIST** the patient willing to make an attempt using counseling and pharmacotherapy to help her quit.
5. **ARRANGE** the follow-up contact, in person or by telephone, preferably within the first week after the quit date.

Usual Care (TTAU): Eligible women randomized to the control group will be informed of the risks of tobacco use and benefits of quitting using the ACOG 5A's approach by their healthcare provider. This standard takes approximately 5-15 minutes, and is offered at each prenatal and postpartum appointment. The research nurse or key personnel will invite participants to complete the tobacco use questionnaires (TUQ), urine cotinine validation, and Expired Air Carbon Monoxide (EACO) analysis to assess ongoing tobacco use at the designated time points; participants will receive a monetary gift card as compensation for their time, at the denominations listed below in Table 1.

The Intervention (ToPIC): Eligible women randomized to the intervention will receive TTAU plus ToPIC administered by the CTTS. At least once monthly, at routinely scheduled prenatal visits or through telephone, the CTTS will provide cessation counseling (see components of a typical counseling session in Box 2). The CTTS will invite participants to complete TUQs, urine cotinine validation and EACO analysis to assess ongoing tobacco use at the designated time points; participants will receive a monetary gift card as compensation for their time. See summary of study procedures in Table 1.

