### Statistical Analysis Plan

Analysis and estimated power: **Primary outcome:** The primary outcome is smoking cessation in the third trimester, defined as urine cotinine level of <100 ng/mL. **Secondary outcomes** include: self-reported number of cigarettes smoked/day, smoking cessation after delivery, infant birth weight, gestational age at delivery, health care utilization outside of scheduled normal prenatal and infant well-child visits. Two-factor mixed models with group by time interactions will be employed to analyze longitudinal continuous data collected over the course of the trial. Significant main and interaction effects will be explored further using Tukey post-hoc tests. Generalized estimating equation (GEE) modeling will be used to test for significant differences between groups and across time for categorical and dichotomous outcomes; these models will also consider possible group by time interactions. Post-hoc analysis of significant main or interaction effects in the GEE models will be accomplished using contrasts. Demographic and personal factors (e.g., maternal age, gestational age at enrollment) may be included as covariates if linked to outcomes in bivariate analysis. We **hypothesize** that compared with the TTAU group, the ToPIC group will have higher tobacco cessation rates, fewer infants born preterm, and fewer ill child health care visits. While we will assess group differences over time

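### No cigarettes-per-day count is scheduled at baseline in either arm, and the SAP commits to no baseline smoking covariate, so this secondary outcome has no starting value

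*Combined protocol and SAP*

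**What the plan says.** Table 1 gives both arms the same baseline measurements: urine cotinine, EACO and the ACOG screen ("ACOG tobacco use screen" in the ToPIC column). The outcome entry for that row is "Eligibility screen for tobacco". The TUQ is listed at 28-34 weeks and at the two postpartum visits, and those three rows carry the outcome "Tobacco cessation or reduction". The paragraphs on usual care and on the intervention say that the TUQ, cotinine and EACO serve "to assess ongoing tobacco use at the designated time points"; Table 1 is where the time points are laid out.

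The ACOG item in Box 1 has five status categories, A to E. The nearest to a quantity is category D: "I smoke now, but I cut down on the number of cigarettes I smoke since I found out I was pregnant".

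The SAP lists "self-reported number of cigarettes smoked/day" as a secondary outcome and analyses continuous longitudinal data with a group-by-time mixed model. Its covariate rule is: "Demographic and personal factors (e.g., maternal age, gestational age at enrollment) may be included as covariates if linked to outcomes in bivariate analysis". The sample-size paragraph after Box 2 makes a firm commitment to demographic covariates only. On entry, Aim 1 says: "All women who report tobacco use would be considered eligible to participate to receive ToPIC or TTAU".

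**The concern.** The protocol concedes, after Box 2, that with two clinics the intervention cannot be fully separated from differences between the clinic populations, and it offers covariate adjustment in response. For cigarettes per day, the most direct such difference is how much the women smoked at entry. Eligibility sets no minimum amount, so it does not limit that difference. Yet no count is scheduled before counselling starts, and no smoking variable is named as a covariate.

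The SAP says its emphasis is on average group differences, to serve as effect sizes for a larger study. For this outcome, the average would include any difference already present at entry, in either direction. A precision gain would also be lost, in a pilot that acknowledges limited power.

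**Working it through.** **Is there a starting count anywhere in the plan?**

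- ACOG screen (Box 1): categories only. Category D records that a woman has cut down, not to what number.
- First TUQ (28-34 weeks): enrolment is before 20 weeks and CTTS contact is at least monthly, so this visit comes after counselling has begun.
- Tobacco history in Box 2: could give a count, but it is counselling content for ToPIC only.
- Cotinine and EACO: measured at baseline in both arms, but on another scale. The SAP names neither as a covariate, and neither as a change outcome.

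That the TUQ holds the cigarettes-per-day item is an inference, since its items are not shown.

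**The plan's own figure for this model.** The SAP states at least 90% power for f = 0.25 with 60 per group. For the group effect under compound symmetry, the noncentrality is f²·N·m/(1+(m−1)ρ), with N = 120 and m visits. The within-woman correlation ρ is not given. With m = 3, the number of visits with a scheduled TUQ, power is 91.4% at ρ = 0.5 and 85.9% at ρ = 0.7. With m = 4 it is 93.0% and 87.0%. The stated figure therefore holds for three visits up to ρ of about 0.5.

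**Effect of an entry difference.** The documents give no SD, correlation or clinic gap, so these are assumptions: 60 per arm, complete normal data, three visits, equal correlation ρ = 0.5 or 0.7 between all visits including baseline, no treatment effect, two-sided 0.05.

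- Variance of the three-visit mean, in SD² units: v = (1+2ρ)/3 = 0.667 (ρ = 0.5) or 0.800 (ρ = 0.7).
- After baseline adjustment: v − ρ² = 0.417 or 0.310. The ratios are 0.625 and 0.388, a cut of 38% or 61%.
- 95% CI half-width, 1.98·√(2v/60): 0.295 or 0.323 SD unadjusted; 0.233 or 0.201 SD adjusted.
- Bias from an entry gap D: ρD if it carries over in proportion to the correlation, D if it persists in full. After adjustment these become 0 and (1−ρ)D.

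Example with D = 0.333, ρ = 0.5 and carry-over: bias 0.167, standard error √(2×0.667/60) = 0.149, noncentrality 1.118, rejection 19.8%.

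| Gap D (SD) | Pattern | Unadjusted, ρ 0.5 / 0.7 | Adjusted, ρ 0.5 / 0.7 |
|---|---|---|---|
| 0.167 | carry-over | 8.6% / 10.9% | about 5% |
| 0.167 | full | 19.8% / 17.3% | 10.8% / 7.8% |
| 0.225 | carry-over | 11.6% / 15.9% | about 5% |
| 0.225 | full | 32.2% / 27.7% | 15.7% / 10.1% |
| 0.333 | carry-over | 19.8% / 29.4% | about 5% |
| 0.333 | full | 60.2% / 52.6% | 28.9% / 16.4% |
| 0.5 | carry-over | 38.4% / 56.6% | about 5% |
| 0.5 | full | 91.4% / 85.9% | 55.7% / 31.0% |

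The adjusted figures ignore a small loss of precision from the baseline imbalance. The adjusted 5% applies only when carry-over equals ρ exactly.

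**What the gaps mean.** A root-mean-square gap D between two clinics corresponds to a within-clinic correlation of (D²/2)/(1+D²/2): 0.014, 0.053 and 0.111 for D = 0.167, 0.333 and 0.5. For normally distributed clinic effects, the median absolute gap is 0.67 of the root-mean-square value. The 0.225 rows are therefore the median case that corresponds to 0.333.

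**Partial remedies at D = 0.333.** If demographic covariates removed 25-50% of the gap, rejection would be 9-19% (carry-over) or 17-38% (full). Suppose baseline cotinine is the only smoking covariate, has correlation k with the count, and relates to follow-up only through the count. It then leaves 1 − k² of the carry-over bias: 84%, 64% or 36% for k = 0.4, 0.6 or 0.8, with 7-24% rejection.

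**The case against.** The strongest reply is that the gap matters little. The outcome is secondary and not among the stated hypotheses, the SAP defines it as a level and not a change, and follow-up levels can be compared without a starting value. The two-clinic limitation is disclosed, and baseline adjustment does not cure it. All of that stands, and it limits the severity.

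Two stronger readings are tempting and are not supported. A reader might infer that self-reported reduction cannot be assessed in TTAU at all. But the ACOG question is repeated at later visits and its category D is itself a self-reported reduction, while change in cotinine or EACO can be calculated in both arms. Only a numeric change in cigarettes per day is out of reach, and a recall item within the TUQ cannot be excluded. A reader might also infer that the main result is compromised, but the primary outcome rests on third-trimester cotinine.

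Table 1 is a summary, and the text groups the TUQ with two tests that are done at baseline, so a baseline TUQ may simply have been left out. That is possible but nowhere stated, and the fix allows for it.

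The SAP's reference to personal factors could admit baseline cotinine, and its examples are not exhaustive. The permission is nevertheless conditional on bivariate results and names no smoking variable, so it is not a commitment.

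Finally, the rejection rates depend on assumed values and on normal, complete data, which is doubtful for cigarette counts in a cessation trial. They show how the problem could act and are not a prediction.

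**Conclusion.** The point holds for cigarettes per day. As written, the plan gives this outcome no starting count in both arms and no committed smoking adjustment, in a comparison where arm and clinic coincide. Under the assumptions above, false rejection without adjustment is 20-29% or 53-60% at a root-mean-square gap of 0.33 SD, and 12-16% or 28-32% at the corresponding median gap of about 0.22 SD (carry-over or full persistence). Adjustment reduces the bias without removing it. The 38-61% variance reduction depends only on the assumed correlation structure and not on any clinic gap. The severity is minor to moderate.

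**What to change.** - Add the TUQ, or a single cigarettes-per-day item, to the baseline row of Table 1 for both arms, completed before any CTTS counselling. If it is already collected, correct Table 1.
- Prespecify baseline cigarettes per day as a covariate for follow-up cigarettes per day, with baseline cotinine as the fallback for women already enrolled.
- Prespecify the already collected baseline cotinine as a covariate for the cessation outcomes. The gain there has not been quantified.
- Use these in place of selecting the smoking covariates by bivariate testing.

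The cost is a few minutes at a baseline visit that is already held and compensated, plus a minor amendment. No new tests or staff are needed. The acknowledged one-clinic-per-arm confounding would be reduced, not eliminated.

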## BOX 2. Typical Counseling Session with a CTTS for Pregnant Women

- Assessment of tobacco use and tobacco use history using an evidence-based tool
- Motivational and practical counseling based on assessment of readiness, including providing education on the maternal and fetal health impacts of smoking
- Provide strong advice to quit as soon as possible
- Exploration of the pros and cons of tobacco use/quitting (decisional balance) and triggers/cues to smoke, including partner smoking and potential engagement in treatment
- Collaboratively developing a tailored treatment plan, which may include but is not limited to incentives, and trigger management strategies, such as stress management or partner support
- Setting a quit date with close follow up
- Discussion relapse prevention strategies during the perinatal and postpartum periods

Our target sample size is 60 participants in each the intervention and control group, for a total of 120 pregnant participants for this pilot project. Additionally, 12 clinic staff and providers will provide quantitative and qualitative data for a mixed-method, multi-stakeholder process evaluation of intervention training and delivery. Due to our limitation of only two participating clinics, we acknowledge that it will not be possible to fully distinguish the effects of the intervention from differences between the two clinic populations. A future larger study of this intervention will include a true group randomized trial, with multiple clinics per treatment, so that the effect of nesting of patients within clinics within treatment will be estimable. In light of this limitation, we will use sample demographic characteristics as covariates in the repeated measures mixed modeling; we acknowledge that the group effects are still likely to be somewhat inflated in this analysis, given the expected artificially small errors due to correlations among patients who visit the same clinic and who may see the same provider. Although we will have limited power, the results from this pilot proof-of-concept study will provide preliminary data to support a highly competitive NIH Health Care Systems Research Pragmatic Trial application.

### Statistical Analysis Plan

Analysis and estimated power: **Primary outcome:** The primary outcome is smoking cessation in the third trimester, defined as urine cotinine level of <100 ng/mL. **Secondary outcomes** include: self-reported number of cigarettes smoked/day, smoking cessation after delivery, infant birth weight, gestational age at delivery, health care utilization outside of scheduled normal prenatal and infant well-child visits. Two-factor mixed models with group by time interactions will be employed to analyze longitudinal continuous data collected over the course of the trial. Significant main and interaction effects will be explored further using Tukey post-hoc tests. Generalized estimating equation (GEE) modeling will be used to test for significant differences between groups and across time for categorical and dichotomous outcomes; these models will also consider possible group by time interactions. Post-hoc analysis of significant main or interaction effects in the GEE models will be accomplished using contrasts. Demographic and personal factors (e.g., maternal age, gestational age at enrollment) may be included as covariates if linked to outcomes in bivariate analysis. We **hypothesize** that compared with the TTAU group, the ToPIC group will have higher tobacco cessation rates, fewer infants born preterm, and fewer ill child health care visits. While we will assess group differences over time

in this way, the emphasis on the analysis will be the detection of average differences between the groups, so that we may use this to estimate effect sizes for a larger study in the future. With 60 participants per group and an alpha level of .05, the power of the repeated measures mixed model F test will have at least 90% power to detect a medium effect in the context of group differences, time differences, or a group by time interaction. A medium effect is such that the ratio of the standard deviation of the group means to the standard deviation of the observations within the populations is at least 0.25. While an effect size driven algorithm for estimating the power associated with GEE models has not been developed, logistic regression is considered as a similar technique. With 120 participants and an alpha level of .05, the power of logistic regression to detect an odds ratio as small as 2.3 will be at least 91%. One way to attain an odds ratio of this magnitude would be if the percent of participants in each group with a particular outcome were 50% versus 30%. The power associated with the corresponding GEE model (and extension of logistic regression to the longitudinal application) is expected to be at least as large, given the additional time points included. Power estimates were obtained using nQuery Advisor, v. 6.02 (Elashoff, J. 1995-2005. nQuery Advisor, Statistical Solutions. Saugus, MA).

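### Primary cessation is a single third-trimester cotinine value with no reference to baseline; unless baseline cotinine gates entry, which the plan leaves open, unequal clinic shares of women already below 100 ng/mL bias the comparison

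*Combined protocol and SAP*

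**What the plan says.** **Outcome.** In the Statistical Analysis Plan, "The primary outcome is smoking cessation in the third trimester, defined as urine cotinine level of <100 ng/mL". No baseline value and no change from baseline enters the definition.

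**Entry.** The Aim 1 paragraph says: "All women who report tobacco use would be considered eligible to participate to receive ToPIC or TTAU". Inclusion criterion 2 in the same paragraph also rests on self-report. Yet participants are told that their "urine will be tested for cotinine to confirm tobacco use at each data collection point", and the baseline row of Table 1 (urine cotinine, EACO and the ACOG questionnaire) carries the outcome label "Eligibility screen for tobacco". Nowhere is there an entry cut-off, a statement of which of the three measures decides, or a consequence of a low result.

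**Analysis.** For yes/no outcomes, GEE models will "test for significant differences between groups and across time for categorical and dichotomous outcomes". Whether baseline is one of the modelled time points is not stated. On covariates, the Statistical Analysis Plan says: "Demographic and personal factors (e.g., maternal age, gestational age at enrollment) may be included as covariates if linked to outcomes in bivariate analysis". The paragraph after Box 2, which concedes that two clinics cannot fully separate intervention from clinic, says: "we will use sample demographic characteristics as covariates in the repeated measures mixed modeling". Baseline cotinine is named in neither place.

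**The concern.** The outcome is a state at one visit, but it is read as cessation, which is a change. The two agree only if every woman starts at or above 100 ng/mL. If entry is by self-report, some women may start below. Those who stay below add to the cessation count in whichever clinic they attend, whatever the counselling did.

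With one clinic per arm, nothing in the design balances the share of such women between arms. A difference in that share passes straight into the unadjusted primary comparison. The plan puts its emphasis on the average group difference and intends to use it to size a larger study. So both the bias and the question of which population the estimate describes would carry forward.

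**Working it through.** **Inputs from the documents.** 60 women per group, and example rates of 50% versus 30% (Statistical Analysis Plan). The plan's odds ratio for that example reproduces: (0.50/0.50)/(0.30/0.70) = 2.33, against a stated 2.3.

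**Assumptions not in the documents.** f is the share below 100 ng/mL at entry (10% and 20% tried). s is the share of those women still below in the third trimester (100%, 80%, 60%). p is the cessation rate among women at or above 100 at entry. The plan gives its example for an unspecified outcome; it is applied here to p. No intervention effect is assumed among women below 100.

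**Formula.** Observed rate = f·s + (1 − f)·p.

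**Unequal shares, no true effect** (p = 0.30 in both groups; f = 0.20 versus 0.10). The difference is 0.10·(s − 0.30):
- s = 100%: 0.44 − 0.37 = 7 points
- s = 80%: 0.40 − 0.35 = 5 points
- s = 60%: 0.36 − 0.33 = 3 points

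**Unequal shares, true effect 0.50 versus 0.30, s = 100%.**
- More such women in TTAU: 0.55 − 0.44 = 11 points
- More such women in ToPIC: 0.60 − 0.37 = 23 points

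**Stratifying at 100 ng/mL by Mantel-Haenszel.** With 12 versus 6 women below and 48 versus 54 at or above, the weights are 12×6/18 = 4.00 and 48×54/102 = 25.41. With no effect, both strata differ by 0, so the result is 0. With the effect, it is 25.41×0.20/29.41 = 17.3 points, whichever clinic has more such women.

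A patient-level simulation (3,000 runs, clustering ignored, no effect, s = 80%) gave a mean difference of 4.8 points unadjusted and −0.2 stratified, with SDs of 8.9 and 8.4 points. Removing the bias therefore cost no precision.

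**Equal shares.** The difference is (1 − f)×20 points at any s: 18 points at f = 10% and 16 at f = 20%. With no true effect it is 0.

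**Equal true shares, precision only** (f = 20%, s = 80%, no effect, rate 0.40 in each group).
- Unadjusted SD: √(2×0.40×0.60/60) = 0.089
- Stratified, with 12 and 48 women per group and weights 6 and 24: √[(6²×2×0.16/12 + 24²×2×0.21/48)/30²] = √(6.00/900) = 0.082

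The gain is therefore from about 9 points to about 8.

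**The case against.** **Entry may already be gated.** Table 1 puts cotinine in an eligibility row, and the Aim 1 text gives confirmation of use as its purpose. A reader might infer from the outcome definition alone that the trial will certainly count unchanged women as quitters. The documents do not support that: if entry requires 100 ng/mL or more, no such woman is enrolled. But they do not establish a gate either, because the written criterion is self-report. This part of the objection stands and makes the point conditional.

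**The covariate rule may cover it.** The examples in the Statistical Analysis Plan are open-ended, and baseline cotinine could count as a personal factor. A simulation of 20% versus 10%, no effect, 2,000 runs, adjusted only when baseline status was linked to outcome (Fisher p < 0.05). For s = 100%, 80% and 60%, the link was found in 100%, 98% and 63% of runs, and mean bias fell from 7.2, 5.1 and 3.1 points to 0.2, 0.1 and 0.8. So the rule would work well if it were applied to baseline cotinine. The plan does not name that variable, makes inclusion optional and ties it to a screen. The remaining gap is commitment, not method.

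**Clinic confounding is already conceded.** It is, but the stated remedy is demographic covariates. Baseline cotinine is a specific measured source, collected in both arms with the same assay as the outcome.

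**The size is unknown.** This is correct. At an equal share of 2% the dilution is 0.4 points, and a 5-point bias is little more than half an SD of the estimate in this pilot.

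**Conclusion.** The point holds conditionally. If baseline cotinine does not gate entry at 100 ng/mL, women already below who stay below are scored as quitters, and unequal clinic shares bias the unadjusted primary comparison. Under the assumed 20% versus 10%, the bias is 3 to 7 points with no true effect. Every magnitude rests on assumed shares, so this is an illustration and not an estimate.

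Three further inferences go too far:
- **That dilution under equal shares makes the result wrong.** It creates no false effect. The smaller difference is the right planning figure for a later study with the same entry rule and outcome; it only needs a label for its population.
- **That chance imbalance is bias.** With a common true share of 10%, 15% or 20%, the counts would differ by 6 or more women in 9%, 16% or 21% of trials. That is sampling variation, already reflected in the standard error; adjustment there gives only the modest precision gain shown.
- **That a yes/no baseline term makes logistic regression unusable if all women below 100 stay below.** Only the coefficient of that term diverges. The group odds ratio remains estimable from women at or above 100.

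The change is worth making because it is nearly free, not because the endpoint has been shown to fail.

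**What to change.** 1. Reconcile the Aim 1 eligibility text with the baseline row of Table 1, and state what the baseline cotinine result is used for. If entry already requires 100 ng/mL or more, say so; the misclassification then does not arise.
2. Otherwise, pre-specify that the primary cessation analysis adjusts for baseline cotinine in all enrolled women, regardless of the bivariate screen. Examples are log baseline cotinine as a covariate, or a Mantel-Haenszel risk difference stratified at 100 ng/mL. The choice between them is the trial statistician's.
3. Report by clinic the number below 100 at entry. Report cessation among women at or above 100 at baseline as a companion result, and label each effect size passed to the larger study by the population it describes.

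**Cost.** Protocol and SAP wording and a little analysis, with no new samples or visits. All enrolled women stay in the primary analysis. The companion set is smaller and less precise: it would omit 12 to 24 of 120 women if 10% to 20% start below 100. The adjustment reduces the clinic confounding that the plan concedes but does not remove it, since clinics may still differ in smoking intensity above 100 and in other respects.

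### Third-trimester cessation is scored on urine cotinine below 100 ng/mL alone, so a woman who reports current smoking at the same time point can count as a quitter

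*Combined protocol and SAP*

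**What the plan says.** The primary outcome in the Statistical Analysis Plan has one component: "The primary outcome is smoking cessation in the third trimester, defined as urine cotinine level of <100 ng/mL". The same paragraph lists "self-reported number of cigarettes smoked/day" separately, as a secondary outcome, together with cessation after delivery, for which it gives no rule of its own.

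Table 1 has one antenatal follow-up row, "28-34 weeks gestation". It schedules urine cotinine, expired-air carbon monoxide (EACO) and the TUQ in both arms, and labels the outcome "Tobacco cessation or reduction". The usual-care paragraph below Box 1 describes the measures as "tobacco use questionnaires (TUQ), urine cotinine validation, and Expired Air Carbon Monoxide (EACO) analysis to assess ongoing tobacco use at the designated time points". Box 1 gives a woman who has reduced but not stopped her own answer: "I smoke now, but I cut down on the number of cigarettes I smoke since I found out I was pregnant".

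No section says how a woman is classified when her questionnaire, cotinine and EACO disagree.

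**The concern.** The procedures treat the urine test as validation, which implies a report to be validated. The primary outcome leaves that report out. Applied exactly, the rule can make the same woman a quitter on the primary outcome and a current smoker on cigarettes per day, at the same time point. This is a classification that the rule produces, and not only a missing detail.

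It concerns follow-up, so a check on cotinine at entry would not repair it. A woman well above 100 ng/mL at baseline could smoke less, say so, and fall below the cut-off.

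The plan says that its emphasis is on average group differences from which to estimate effect sizes for a larger study. An estimate that mixes quitting with reduction could mis-size that study. ToPIC adds counselling by the tobacco treatment specialist (CTTS) at least monthly, so more sub-threshold smoking in that arm is plausible. The documents do not establish it.

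**Working it through.** **Inputs from the documents.** Cut-off 100 ng/mL; 60 women per group ("Our target sample size is 60 participants in each the intervention and control group"); alpha 0.05, taken as two-sided because the side is not stated; illustrative rates of 50% v 30%.

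**Assumed inputs, not in the documents.** *q* is the true quit rate. *r* is the share of continuing smokers with cotinine below 100. Every true quitter is taken to be below 100 and to report not smoking.

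**The plan's own figures.** For 50% v 30% the odds ratio is (0.50/0.50)/(0.30/0.70) = 2.33, which agrees with the plan's 2.3. The stated power of at least 91% is not reproduced: a two-group comparison with 60 per group gives 61%. That is a separate matter, and this point does not depend on it, but 61% is the reference for the power figures below.

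**Formulas.** Under cotinine alone, the scored rate is *q* + (1 − *q*)*r*. Power for two proportions is Φ{[d − 1.96√(2p̄(1 − p̄)/60)] / √([p₁(1 − p₁) + p₂(1 − p₂)]/60)}, where d is the difference and p̄ the mean of the two rates. Clustering by clinic is ignored.

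**Equal shares, true effect 50% v 30%.**

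| *r* in both arms | ToPIC | TTAU | Power |
|---|---|---|---|
| 0% | 50% | 30% | 61% |
| 10% | 0.50 + 0.50 × 0.10 = 55% | 0.30 + 0.70 × 0.10 = 37% | 51% |
| 20% | 0.50 + 0.50 × 0.20 = 60% | 0.30 + 0.70 × 0.20 = 44% | 42% |

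At *r* = 10% the odds ratio falls from 2.33 to (0.55/0.45)/(0.37/0.63) = 2.08.

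**Unequal shares, true quitting 30% in both arms.**

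| *r*, ToPIC v TTAU | Scored cessation | Odds ratio |
|---|---|---|
| 5% v 5% | 33.5% v 33.5% | 1.00 |
| 10% v 5% | 37% v 33.5% | 1.17 |
| 15% v 5% | 40.5% v 33.5% | 1.35 |
| 20% v 5% | 44% v 33.5% | 1.56 |
| 25% v 5% | 47.5% v 33.5% | 1.80 |

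For 20% v 5%: 0.30 + 0.70 × 0.20 = 0.44; 0.30 + 0.70 × 0.05 = 0.335; (0.44/0.56)/(0.335/0.665) = 1.56. The chance of a significant result favouring ToPIC is Φ[(0.105 − 0.1743)/0.0884] = Φ(−0.784), about 22%, against the nominal 2.5%. It is 12% for 15% v 5% and 34% for 25% v 5%.

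**With reported non-smoking also required.** The scored rate becomes *q* + (1 − *q*)*rc*, where *c* is the proportion of sub-100 continuing smokers who conceal their smoking. With accurate reports (*c* = 0), every row of the second table becomes 30% v 30%.

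**The case against.** The strongest objection is that self-report can bring in a bias that cotinine does not have. The CTTS who counsels ToPIC women also invites them to complete the TUQ; in TTAU a research nurse or key personnel does so. Take 30% true quitting and *r* = 20% in both arms. Cotinine alone scores 44% v 44%, which is no false effect. If half of the sub-100 continuing smokers in ToPIC conceal their smoking and none in TTAU do, the combined rule scores 0.30 + 0.70 × 0.20 × 0.50 = 37% v 30%, odds ratio 1.37. This stands, and it is the reason to report both definitions. It does not make cotinine alone the better primary rule in every case: with shares of 20% v 5%, the same concealment again gives 37% v 30%, a gap of 7 points against 10.5 under cotinine alone. The combined rule also never scores a concealing smoker more leniently than the present rule does.

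Other parts of the objection also stand. The quit rates and shares are assumptions. The TUQ items are not shown; that it asks about current smoking is inferred from the cigarettes-per-day outcome. That secondary outcome makes discordance visible in the data, though it does not change how the primary outcome is scored. The Table 1 label and the Box 1 answer are only supporting context, since neither defines an outcome.

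A reader might infer that any cutting down counts as cessation. It does not: a woman who cuts down but stays at or above 100 is scored as not having quit. A reader might also infer that the rule must favour ToPIC. That needs a larger sub-threshold share in ToPIC, which the documents do not show.

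**Conclusion.** The point holds as a defect in the definition: followed exactly, the primary outcome scores some women who report current smoking as having quit. That much rests on the text, together with the inference that the TUQ records current smoking and that the third-trimester assessment is the 28-34 week row.

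The size and direction of the effect are unknown. Equal shares dilute a real effect (55% v 37% in place of 50% v 30% at a 10% share). A larger share in ToPIC creates an apparent one (odds ratios of 1.17 to 1.80 over the assumed range, with 30% true quitting in both arms). The documents do not support a claim that the result will be inflated. The change is worth making before analysis because the pilot is meant to supply an effect size for quitting and the data needed are already scheduled.

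**What to change.** In the Statistical Analysis Plan, define third-trimester cessation as no current smoking reported on the TUQ **and** urine cotinine below 100 ng/mL at the same 28-34 week time point. Apply the same rule to cessation after delivery. Report cotinine below 100 alone beside it as a prespecified sensitivity analysis. Use EACO as an additional check only if the sponsor prespecifies a cut-off, since the documents give none. The text should also state the period that the TUQ answer covers and how a woman with only one of the two results is classified.

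The cost is wording and one further analysis; no new measurement is needed. The downsides to state are slightly lower cessation rates, and possible differences in concealment between arms because different staff invite the questionnaire. If the two definitions give different group effects, the report should say so and should not rest on either alone.
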